8.0 Statistical Considerations

8.1 General Statistical Considerations

All registry participants who are consented will be included in analyses. Descriptive tabular and graphical summaries of data will be used to characterize time-to-event outcomes such as survival and time to VAD implantation and profiles of continuous outcomes such as QOL scores and 6-minute walk test distance over time. For categorical variables, frequencies and percentages will be presented. For continuous variables, the number of subjects, mean, standard deviation, minimum, 25th percentile, median, 75th percentile and maximum will be presented. Continuous data subject to censoring (i.e., time-to-event data) will be summarized by the 25th percentile, median and 75th percentile, when estimable from the Kaplan-Meier estimates.

Statistical models will be employed to estimate important features of outcomes, as well as to understand the impact of important covariates (such as biomarkers) on these outcomes. The models considered for use in these analyses allow for a missing at random (MAR) mechanism. MAR means that the missing values mechanism can be explained by observed data (e.g., past values of covariates and outcomes) and does not depend on the unobserved values of outcome measures. However, some participants may dropout from the study due to unobserved factors related to the outcome itself; for example, sicker participants may be more likely to dropout than healthier patients and so we lack survival information on those sicker patients. If we suspect such bias is present, the methods which assume MAR are not applicable. Instead we would need to use methods that model the missing data mechanism itself to achieve valid inferences. We will incorporate plausible missing values mechanism into the model as discussed in Little^[28] and investigate how such mechanism may affect the estimates of prognostic factors. To this end, sensitivity analyses will be conducted involving selection and/or pattern-mixture models with an appropriate sub-model used to describe dropout.^[29]

Model assumptions will be thoroughly checked using informal (e.g., inspection of residuals) and formal methods (e.g., score test for extra parameters or methods based on likelihood displacement). If individual outliers are detected, their influence will be evaluated using influence diagnostics methods based on comparing estimates from models fitted to data with and without outlying values. Whenever we are not successful in fitting the parametric models (linear or non-linear), then non-parametric analyses and/or transformation of the variables involved in the analysis will be considered.

Two-sided testing will be conducted using a nominal significance level of 0.05 for all tests. No adjustments for multiplicity will be applied. Further details of the analyses will be documented in the Statistical Analysis Plan.

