8.3.3 Modeling of Clinical Outcomes

We seek to estimate the morbidity and mortality rates in this population and to evaluate the effectiveness of baseline factors in determining their prognosis. To accomplish this goal [objective 1], we will use logistic regression for dichotomous outcomes (e.g., proportion of subjects with an interest in VAD therapy), Poisson regression for count outcomes (e.g., number of hospitalizations per participant), Cox proportional hazard models for time-to-event outcomes (e.g., survival, time to VAD implantation) and linear mixed-effects models for continuous outcomes (e.g., quality of life, functional capacity)^[30-32]. For time-to-event outcomes, survival time will be defined as the time from consent to the event or, for participants who did not experience an event, to the last study visit. Given the potentially small number of events, differences between groups will be tested by means of the log rank test. For longitudinal continuous outcomes, we will model correlated errors with a first order autoregressive (AR1) process since it is reasonable to assume adjacent values are more correlated than observations father apart in time. Alternative variance-covariance structures will be investigated, if needed.

Univariable models will be developed first, using baseline characteristics as the predictors. Multivariable models will be built incorporating known prognostic factors (i.e., those identified in the literature) and those suggested from the univariable analyses (i.e., those with p<0.10). Given the sample size and the potential for small numbers of events (in time-to-event outcomes), we will apply the principle of parsimony to the number of potential prognostic factors included in the ultimate model. In addition to using such standard methods to develop multivariable risk prediction models, we will derive simplified scoring systems to aid in clinical decision-making. Alternative classification schemes (e.g., CART) will be employed as sensitivity analyses. To assess the performance of the risk prediction models, we will evaluate their calibration (or reliability) discrimination and accuracy^[33].

Comparison among existing classification systems and the use of second early assessments (baseline B measures instead of baseline A measures) with the improved risk prediction model(s) developed above will be based on the concordance index, parsimony of the model, and the other performance metrics described above^[34].

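### The claim that the models allow missing-at-random dropout is right for the mixed models but not for the Cox and log-rank analyses, which need censoring independent given baseline

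*Protocol*

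**What the plan says.** Section 8.1, in its paragraph on statistical models, states: "The models considered for use in these analyses allow for a missing at random (MAR) mechanism". It explains that under MAR the mechanism "can be explained by observed data (e.g., past values of covariates and outcomes") and does not depend on unobserved outcome values. It then gives the case where this fails, dropout from unobserved factors related to the outcome: "sicker participants may be more likely to dropout than healthier patients and so we lack survival information on those sicker patients". For that case it commits to sensitivity analyses with selection and/or pattern-mixture models.

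The time-to-event methods are:
- Section 8.3.3 names "Cox proportional hazard models for time-to-event outcomes (e.g., survival, time to VAD implantation").
- On predictors it says: "Univariable models will be developed first, using baseline characteristics as the predictors".
- Follow-up time runs from consent to the event or, "for participants who did not experience an event, to the last study visit".
- Because events may be few, "differences between groups will be tested by means of the log rank test".
- Section 8.1 summarises event times by quartiles, "when estimable from the Kaplan-Meier estimates".

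Section 5.3 asks sites to record whether a participant who withdraws still allows outcome follow-up at Month 24.

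**The concern.** The MAR sentence covers all the models, but the property belongs to only some of them. A likelihood-based mixed model for walk distance or quality of life contains the participant's earlier values, so dropout that depends on those values can be ignored. A Cox model on baseline characteristics does not contain the 6- or 12-month visit. A participant who declines visibly at month 6 and then stops attending leaves the risk set, and those who remain with the same baseline profile stand in for that participant although they are on average healthier.

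Section 8.1 sorts dropout into two kinds: explained by observed data, hence covered, and due to unobserved factors, hence sent to sensitivity analysis. Loss after an observed decline falls into the first kind, so for survival neither the main analysis nor the named sensitivity analyses are directed at it.

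At stake are the absolute 2-year risks and the risk-prediction tools of Objective 1. Calibration checked in the same censored data inherits the error and cannot reveal it.

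**Working it through.** **1. What each analysis needs**

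| Analysis | Information used | Dropout it tolerates |
|---|---|---|
| Linear mixed model (8.3.3) | baseline and all earlier outcomes | depends on that observed history: MAR as 8.1 defines it |
| Cox on baseline predictors (8.3.3) | baseline only | independent of the event given those predictors |
| Log-rank (8.3.3) | group only | independent of the event within each group |
| Kaplan-Meier (8.1) | none | independent of the event |

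Dropout driven by a decline seen at a follow-up visit meets the first row and fails the other three.

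**2. The plan's own figures (section 8.2)**

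Year-2 sample: 400 × (1 − 0.30) = 280. Half-width: 1.96 × √(p(1−p)/280) = 2.55% at p = 5% and 5.86% at p = 50%. The stated 2.6% and 5.9% reproduce. The same formula gives 4.7 points at 20% and 5.4 at 30%. The 30% covers outcomes such as death or VAD together with dropout and is not split, so every hazard below is an assumption.

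**3. Size for Kaplan-Meier, solved numerically**

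All participants start stable. An observed decline occurs at rate λ = 0.35 per year. The death hazard is h0 before and h1 after decline, and the dropout hazard is c0 before and c1 after. Dropout depends only on the observed state. With a = λ + h0 + c0 and b = h1 + c1, the shares still under observation are

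p0(t) = exp(−at), p1(t) = λ/(b−a) × [exp(−at) − exp(−bt)].

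- True 2-year mortality: 1 − p0(2) − p1(2) with c0 = c1 = 0.
- Kaplan-Meier limit: 1 − exp(−∫ (h0·p0 + h1·p1)/(p0 + p1) dt) over 0 to 2 years.

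For h0 = 0.07 and h1 = 0.45, the true value is 1 − [e^−0.84 + (0.35/0.03)(e^−0.84 − e^−0.90)] = 27.5%. Multiplying both death hazards by 0.6 (0.042 and 0.27) gives 18.15%.

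| h0 / h1 | c0 / c1 | Dropout | Observed deaths + dropout | True | Kaplan-Meier | Shortfall (points) |
|---|---|---|---|---|---|---|
| 0.042 / 0.27 | 0.02 / 0.12 | 7.7% | 24.7% | 18.15% | 17.75% | 0.4 |
| 0.042 / 0.27 | 0.02 / 0.20 | 10.7% | 27.1% | 18.15% | 17.44% | 0.7 |
| 0.042 / 0.27 | 0.03 / 0.24 | 13.3% | 29.4% | 18.15% | 17.33% | 0.8 |
| 0.07 / 0.45 | 0.04 / 0.40 | 17.7% | 40.8% | 27.50% | 25.62% | 1.9 |

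The first three rows respect the plan's 30%; the last does not. Half-widths at n = 400 are 1.96 × √(0.1815 × 0.8185/400) = 3.8 points and 1.96 × √(0.275 × 0.725/400) = 4.4 points.

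**4. Does baseline adjustment help?**

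A simulation of 100,000 participants over 24 months added a binary baseline factor that doubles the decline and death hazards. Stratifying on it stands in for a model on baseline predictors.

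- Monthly hazards: decline 0.015; death 0.004 before and 0.015 after decline; dropout 0.002 and 0.02. Dropout was 10.9% and observed deaths plus dropout 29.5%. True mortality was 20.3%, baseline-adjusted 19.7%, Kaplan-Meier 19.7%, weighted on the observed history 20.3%.
- Death 0.003 and 0.03, dropout 0.002 and 0.04. Dropout was 14.7% and the sum 35.3%. True 24.8%, baseline-adjusted 22.5%, Kaplan-Meier 22.3%, weighted 24.8%.
- As the second, with post-decline dropout 0.08. Dropout was 21.2% and the sum 39.2%. True 24.8%, baseline-adjusted 20.5%. This lies far outside the plan's expectation.
- Dropout unrelated to decline (0.006 in both states): every method returned 24.8%.

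Baseline adjustment removes almost none of the bias. Weighting on the observed history removes it.

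**The case against.** The best defence is that section 8.1 already sees the problem. It names sicker participants leaving and survival information being lost, says MAR methods do not apply in that case, and states that sensitivity analyses will be conducted. Kaplan-Meier stands in the preceding, descriptive paragraph, so the MAR sentence arguably does not cover it. Month 24 follow-up recovers outcomes for withdrawn participants who agree. The expected bias is smaller than the sampling error, and the details of censoring models belong in the SAP.

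Much of this stands. The Kaplan-Meier summaries share the assumption but are not the main target. Month 24 follow-up reduces the bias, though not for participants who are lost or who refuse. The size is modest. What the defence does not repair is the sentence itself, which is wrong for the Cox models within its own paragraph. The protection that follows is aimed at unobserved causes. This is a positive statement that an SAP would inherit, not a detail left open.

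A reader might infer three stronger points that the protocol does not support:
- That selection and pattern-mixture models cannot handle event times. They can: raising the hazard after dropout is a pattern-mixture analysis.
- That the sensitivity analysis happens only on suspicion. The text can be read that way, but it also contains a flat commitment.
- That survival is the designated main outcome. The study summary and section 3.2 list five outcomes and name no primary.

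**Conclusion.** The MAR statement is too broad. It holds for the linear mixed models and fails for the Cox, log-rank and Kaplan-Meier analyses when dropout follows an observed post-baseline decline.

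The downward direction rests on the assumption that decline raises both dropout and death. This fits the plan's remark about sicker participants, although that remark is tied to unobserved factors. The size cannot be derived from the protocol. Under the assumed hazards it is about 0.4 to 0.8 points at 8-14% dropout within the plan's 30%, and about 2 points at 18% dropout with higher mortality. Both are below the half-width, and Month 24 follow-up lowers them further. It would be wrong to conclude that mortality will be materially understated. The error is nevertheless systematic, the confidence interval does not reflect it, and the data to correct it are already being collected.

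**What to change.** 1. In section 8.1, limit the MAR sentence to the likelihood-based mixed models.
2. State that the Cox analyses assume censoring independent of the event given the included predictors, the log-rank test within group, and Kaplan-Meier unconditionally.
3. Add an inverse-probability-of-censoring-weighted analysis, or a joint model, for the time-to-event outcomes. Use the serial 6MWT, KCCQ, NYHA class and INTERMACS profile, and interim hospitalizations.
4. State that the planned not-at-random sensitivity analysis is run for event times regardless of suspicion, for example as a pattern-mixture shift of the post-dropout hazard by stated factors such as 1.5, 2 and 3.

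Cost: protocol or SAP wording, additional programming and slightly wider intervals from weighting. No new data, visits or participants are needed.

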8.2 Sample Size Considerations

The sample size for this prospective cohort (registry) study is based primarily on logistical considerations. It is anticipated that 400 eligible subjects will be enrolled in the study in the 12-month recruitment period. We predict that 30% of the 400 enrolled participants will achieve clinical outcomes such as death or VAD, or will drop-out during the 2-year study follow-up. Thus, we project that 280 participants will provide year 2 data and we provide the degree of precision with which we can estimate the important clinical outcomes using the conservative estimate of 280 registry participants. A sample of 280 participants will provide precision (half-width of a 95% confidence interval, based on normal approximation; East v6.3; Cytel Inc., 2014) ranging from 2.6% to 5.9% for true incidence rates ranging from 5% to 50% (where precision is minimal), respectively. Figure 3 below shows the correspondence of precision and true proportion of participants. The precision of estimation is improved with the use of time-to-event methods instead of the simpler binomial approach used in the calculations above.

Figure 3: Correspondence of precision and true proportion of participants experiencing clinical outcomes in the 2-year study period for sample size of 280 participants.

8.3 Analysis Approach

8.3.1 **Demographic and Baseline Characteristics**

We will present descriptive statistics for demographic and baseline patient characteristics as described above [objective 1]. We will compare these characteristics for those who dropout and those who do not dropout using two-sample t-tests or Wilcoxon rank sum tests for continuous variables and Chi-square or Fisher's exact tests for discrete variables.

8.3.2 Characterization of Clinical Outcomes and Other Outcomes

We will present descriptive statistics for clinical outcomes [objective 1] and other outcomes measured over time (e.g., patient preferences [objective 2], caregiver burden [objective 3]). In addition, exploratory analyses will be performed to better understand the characteristics of different definitions of health utility measures (e.g., EQ-5D VAS or EQ-5D index scores) incorporated into a composite endpoint that includes survival without heart transplant and MCSD.

8.3.3 Modeling of Clinical Outcomes

We seek to estimate the morbidity and mortality rates in this population and to evaluate the effectiveness of baseline factors in determining their prognosis. To accomplish this goal [objective 1], we will use logistic regression for dichotomous outcomes (e.g., proportion of subjects with an interest in VAD therapy), Poisson regression for count outcomes (e.g., number of hospitalizations per participant), Cox proportional hazard models for time-to-event outcomes (e.g., survival, time to VAD implantation) and linear mixed-effects models for continuous outcomes (e.g., quality of life, functional capacity)^[30-32]. For time-to-event outcomes, survival time will be defined as the time from consent to the event or, for participants who did not experience an event, to the last study visit. Given the potentially small number of events, differences between groups will be tested by means of the log rank test. For longitudinal continuous outcomes, we will model correlated errors with a first order autoregressive (AR1) process since it is reasonable to assume adjacent values are more correlated than observations father apart in time. Alternative variance-covariance structures will be investigated, if needed.

Univariable models will be developed first, using baseline characteristics as the predictors. Multivariable models will be built incorporating known prognostic factors (i.e., those identified in the literature) and those suggested from the univariable analyses (i.e., those with p<0.10). Given the sample size and the potential for small numbers of events (in time-to-event outcomes), we will apply the principle of parsimony to the number of potential prognostic factors included in the ultimate model. In addition to using such standard methods to develop multivariable risk prediction models, we will derive simplified scoring systems to aid in clinical decision-making. Alternative classification schemes (e.g., CART) will be employed as sensitivity analyses. To assess the performance of the risk prediction models, we will evaluate their calibration (or reliability) discrimination and accuracy^[33].

Comparison among existing classification systems and the use of second early assessments (baseline B measures instead of baseline A measures) with the improved risk prediction model(s) developed above will be based on the concordance index, parsimony of the model, and the other performance metrics described above^[34].

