4.3 Maximal Oxygen Consumption (peak VO₂)

Maximal treadmill cardiopulmonary exercise tests (CPX) will be done for consented heart failure subjects at the baseline B visit. Maximal oxygen consumption (peak VO₂) during treadmill CPX is the most objective and well-validated measure of functional capacity.^[23] Its depression reflects the impaired ability to increase cardiac output and is an integrated measure of the cardiac, pulmonary, vascular and muscular abnormalities that characterize heart failure. While not completely effort-dependent, the adequacy of the effort as maximal can be determined.

The reliability of peak VO₂ measurement in the setting of stable outpatients with chronic heart failure has recently been assessed in 398 subjects participating in an HF-ACTION sub-study with test-retest measurements 1-2 weeks apart.^[24] The difference (mean \pm SD) in peak VO₂ measurement was 0.0±1.3 ml/min/kg (10th,90th percentile = 0.1,3.0) with nominal increases in 46% and decreases in 48% of subjects. This SD of 1.3 represented 9% of the mean peak VO₂ of these subjects. These data demonstrate the reproducibility of the peak VO₂ measurement and support the strategy of using a single measurement of peak VO₂ as an eligibility criterion in REVIVAL.

Maximal treadmill cardiopulmonary exercise testing is invaluable in the assessment of functional limitations imposed by heart failure and in predicting survival in patients referred for cardiac transplant evaluation. ^[19] [name] performed the landmark study demonstrating the utility of a peak VO₂ threshold of 14 ml/min/kg for selecting heart transplant candidates.^[25] At Columbia University, 396 patients age 65 years or older (mean + SD = 70±5) with systolic (80%) or diastolic heart failure (LVEF 30±15%, peak VO₂ 13.9±4.4 ml/min/kg) were followed until death (35%), urgent transplantation (8.8%), LVAD (3.0%) or elective transplantation (2.3%). Overall 1-year event-free survival was 81%. As seen in Figure 2, individuals with peak VO₂ 10-14 ml/min/kg and < 10 ml/min/kg had event-free survivals of ≈78% and ≈70% at 1-year and ≈60% and ≈45% at 2-years, respectively.^[26]

Figure 2: individuals with peak VO₂ 10-14 ml/min/kg and < 10 ml/min/kg had event-free survivals of \approx 78% and \approx 70% at 1-year and \approx 60% and \approx 45% at 2-years, respectively.

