4.13 Heart Failure Survival Score (HFSS)

The HFSS will be calculated by the Data Coordinating Center using data collected at baseline B. Instructions relevant to the calculation will be included in the MOP.

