6.2 Study Procedures and Assessments

6.2.1 Baseline A

Initiation of baseline A will occur with the heart failure subject signing the Informed Consent document(s). Standard of Care (SOC) testing will be included in the heart failure subject evaluation for this visit. All SOC procedures are labeled as such below. All other procedures will be research expenses. After signing the informed consent document(s), subjects will undergo the following testing and evaluation:

- 1. Directed history and physical (including NYHA and INTERMACS Patient Profile)
- 2. ECG (SOC)
- 3. Blood draw for:
 - a. CBC with platelets and differential count [SOC]
 - b. Comprehensive metabolic panel [SOC]
 - c. Uric Acid
 - d. Total cholesterol
 - e. INR
- 4. Handgrip strength (by dynamometer)
- 5. Gait Speed Test
- 6. 6 minute walk test
- 7. Quality of life and health utility questionnaires
- 8. Patient preference questionnaire
- 9. Caregiver participation overview with heart failure subject
- 10. Dispense patient diary

If the heart failure subject has an historic ECG on file that was completed within 30 days of the assessment date, this may be used for fulfillment of this visit requirement if, in the opinion of the investigator, the historic ECG is highly likely to represent the subject's current health status.

If the heart failure subject has historic laboratory results on file that were drawn within 14 days of the assessment date, these results may be used for fulfillment of this visit requirement if, in the opinion of the investigator, the historic laboratory result(s) are highly likely to represent the subject's current health status.

Baseline A procedures should be completed within two weeks of consent. The baseline B visit should be scheduled to occur two (2) months (\pm 30 days) after consent.

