Appendix A: Time and Event Schedule

Event/Assessment	Baseline A	Baseline B*	+/- 45 days			+/- 30 days
			6-Month Visit	12- Month Visit	18- Month Visit	24-Month Visit
6-Minute walk test	Х	Х	Х	Х	Х	X
Blood draw – Labs	X**	X**	Х	X**	Х	Х
Blood draw – Biomarker and Genetic testing		X				
Caregiver questionnaire		Х	Х	Х	Х	Х
Concomitant Medication	Х	Х	Х	Х	Х	Х
Demographics	Х					
Directed history and physical exam (including NYHA and INTERMACS profiles)	X	X	x	X	X	X
Dispense Patient Diary	Х					
ECG	Х	Х		Х		
Gait speed test	Х	Х	Х	Х	Х	Х
Handgrip strength test	Х	Х	Х	Х	Х	X
Heart Failure Survival Score (HFSS)		X				
Maximal treadmill CPX test		X				
QOL and health utility questionnaires	х	Х	X	Х	X	Х
Seattle Heart Failure Model (SHFM) Score ***	Х	X		Х		
Transthoracic Echo		X				
Outcome assessments		Х	Х	Х	Х	Х

*To take place 8 weeks (+/- 30 days) after consent **In addition to standard of care labs (CBC and Comprehensive Metabolic Panel) study-specific (nonstandard of care) labs are uric acid, total cholesterol and INR

*** Calculated and entered by DCC

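### Models that use baseline B predictors run on a clock started at consent, so 1 to 3 months in which no terminal event can occur are counted as time at risk

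*Protocol*

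**What the plan says.** Section 8.3.3 defines the clock for all time-to-event outcomes: "survival time will be defined as the time from consent to the event", or to the last study visit if no event occurs. Model building begins with baseline variables and does not distinguish the two baseline visits: "Univariable models will be developed first, using baseline characteristics as the predictors". The section then sets the improved risk models against existing classification systems and "the use of second early assessments (baseline B measures instead of baseline A measures", judged on the concordance index, parsimony and the other performance metrics, which include calibration.

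Baseline B comes later than consent. Section 6.2.1: "The baseline B visit should be scheduled to occur two (2) months" after consent, ± 30 days. Appendix A: "To take place 8 weeks (+/- 30 days) after consent". Several candidate predictors are study measurements made only at that visit:

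- Exercise testing (Section 4.3): "Maximal treadmill cardiopulmonary exercise tests (CPX) will be done for consented heart failure subjects at the baseline B visit".
- HFSS (Section 4.13): "The HFSS will be calculated by the Data Coordinating Center using data collected at baseline B".
- Core-laboratory echocardiography (Section 4.4) and the biomarker blood draw (Section 4.17).

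Under Section 3.2, death, transplant and durable VAD end follow-up, and outcomes are collected at every visit after baseline A. Section 8.1 says all consented participants are analysed. The protocol mentions no landmark, delayed entry or second time origin.

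**The concern.** A predictor measured at baseline B can be observed only in someone who reaches baseline B. On a clock started at consent, that person's first 1 to 3 months cannot contain a death, transplant or durable VAD, yet they count as time at risk. This is immortal time. The people who did have such an event in that window have no baseline B values, so their events count only in baseline A models.

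Hospitalization and stroke behave differently. They do not remove the participant, but one that occurs before baseline B precedes the predictor meant to forecast it, and the predictor may partly reflect it.

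The outputs at stake are named in Objective 1: better risk prediction tools, whether the two-month assessment adds prognostic value, and calibration and discrimination of existing systems. Section 8.3.3 also plans simplified scores for clinical decision-making, which depend on absolute risk.

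**Working it through.** **Inputs.** N = 400 and a 30% two-year proportion with a clinical outcome or drop-out (Section 8.2). Baseline B at m = 2 months, range about 1 to 3 (Section 6.2.1, Appendix A). Follow-up 24 months (Section 3.2).

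**The plan's own figure.** Section 8.2 takes n = 400 × (1 − 0.30) = 280. The half-width is 1.96 × √(p(1 − p)/280): 2.55% at p = 5% and 5.86% at p = 50%. These reproduce the stated 2.6% and 5.9%. They do not bear on the time origin; Section 8.2 matters here as the source of the 30%.

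**Size of the early loss.** The protocol gives no early event rate, so two assumptions are made: a constant hazard, and the whole 30% treated as terminal events.

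- Monthly hazard: h = −ln(0.70)/24 = 0.01486.
- Event before baseline B: 1 − exp(−hm). For m = 2 this is 2.93%, and 400 × 0.0293 = 11.7 participants. For m = 1 it is 5.9 and for m = 3 it is 17.4.
- Share of the 24-month events at m = 2: 11.7/120 = 9.8%.

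**Effect on absolute risk.** True risk to month T is 1 − exp(−hT). Among baseline B attenders on the consent clock it reads 1 − exp(−h(T − m)).

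- T = 12, m = 2: 1 − exp(−10h) = 13.8% against 1 − exp(−12h) = 16.3%. For m = 1 to 3 the reading is 15.1% to 12.5%.
- T = 24, m = 2: 1 − exp(−22h) = 27.9% against 30%. For m = 1 to 3 the reading is 29.0% to 26.8%.

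**Other two-year terminal event rates, m = 2.**

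| Two-year rate | Events before B (of 400) | 12-month risk, B attenders v true | 24-month risk, B attenders v true |
|---|---|---|---|
| 20% | 7.4 | 8.9% v 10.6% | 18.5% v 20% |
| 30% | 11.7 | 13.8% v 16.3% | 27.9% v 30% |
| 50% | 22.5 | 25.1% v 29.3% | 47.0% v 50% |

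**Effect on relative measures.** These come from 300 simulated cohorts of 400, with baseline B uniform over 1 to 3 months, a correlation of 0.7 between the A and B predictor values, and a log hazard ratio of 0.7 for the current value. On average 11.9 participants per cohort had an event before baseline B. The Cox log hazard ratio for the B predictor was 0.710 from consent and 0.710 with delayed entry at B. The concordance of the same baseline A predictor was 0.636 in all participants and 0.629 in those reaching baseline B. It moves because the set of participants and events changes, not because the predictor does.

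**The case against.** **Relative effects barely move.** This stands. In the simulation the log hazard ratio does not change to three decimals, and the change in concordance is 0.007. A reader might infer that screening and ranking of prognostic factors are distorted; the calculation does not support that.

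**Consent is not a wrong time scale in itself.** This stands. Consent remains usable for baseline B models if participants enter the risk set at baseline B. The fault is a consent origin with no entry time for later-measured predictors.

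**The lower figure can be read as valid.** This stands in part. The 13.8% is correct as the risk by month 12 after consent for someone already known to reach baseline B at month 2. It is too low as a 12-month risk from baseline B, or as the risk from consent for everyone enrolled, and a clinical score would naturally be read in one of those ways.

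**Only terminal events are excluded by construction.** This stands. A reader might infer that attenders were free of every study outcome. Section 3.2 stops follow-up only for death, transplant and durable VAD.

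**Existing scores can be compared fairly.** This stands. A reader might infer that SHFM at baseline A will be set against HFSS at baseline B. Section 8.3.3 names no such pairing, and Section 4.12 and Appendix A have SHFM calculated at baseline B too, so both scores are available at one visit.

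**The analysis of all consented participants, the missing-at-random models or the SAP may deal with this.** This does not stand. Values at baseline B for someone who died before it do not exist, and imputing them would predict an event from a measurement dated after it. The SAP is not at hand, but a landmark written there would conflict with the origin that Section 8.3.3 states for all time-to-event outcomes.

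**Conclusion.** The point holds for time-to-event models and scores that use a baseline B predictor. Absolute risk and calibration for terminal events are biased low, and A-versus-B performance comparisons rest on different participants and events. Baseline-A-only models and overall event rates are not affected.

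The size is moderate: about a tenth of the two-year terminal events fall before a two-month baseline B, and risk is understated by about 2.5 percentage points at 12 months and 2 points at 24 months. These figures rest on a constant hazard and on counting all of the 30% as terminal events. Because the 30% includes drop-out, 12 early events may be too many; a 20% rate gives about 7 and a 50% rate about 22. A hazard concentrated soon after consent would raise the number.

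This should be fixed, but it does not undermine the study. The registry is observational, its specific analyses are described as hypothesis-generating, and the data needed for the repair are already collected.

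**What to change.** Add to Section 8.3.3, and carry into the SAP:

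- For any time-to-event model or score that uses a baseline B predictor, either start time at the baseline B visit (landmark) or keep the consent scale with delayed entry at that visit. Count only later events. Both options remove the bias.
- For A-versus-B comparisons, evaluate the baseline A comparators, including SHFM, in the same participants with the same origin or entry time.
- Report how many participants have an event before baseline B, by type.
- Keep consent as the origin for overall event rates and baseline-A-only models.

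The cost is a few lines of text and no new data. The downside is that events before baseline B inform only the baseline A models and the overall rates.
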